The PROMIS Physical Function Scale measures self-reported ability, this includes the functioning of upper and lower extremities as well as activities of daily life.

The PROMIS Depression Questionnaire measures self-reported negative mood, views of self, and decreased positive mood and engagement.

3. Communication Questionnaire. Use of CG-CAHPS Surveys for Primary Outcome (IR-5). We will evaluate patient experience data as measured by Clinician and Group Consumer Assessment of Healthcare Providers and Systems (CG-CAHPS) Adult 6-Month Visit survey (version 3.0) that is already being collected by the Cedars-Sinai Medical Network. Use of CG-CAHPS will ensure generalizability of the results, as many health systems rely on the survey to assess patient satisfaction. Broadly, CAHPS surveys are premised upon systematic and standardized measurement and are widely regarded as the national standard for collecting and reporting information from patients about care experiences. CG-CAHPS asks patients to report on their experiences with healthcare providers from their most recent office visit using items related to physician-patient communication. CG-CAHPS is itself widely used, tested, and validated, featuring prominently in CMS's Value-Based Purchasing (Pay for Performance) initiatives.¹³³ In studies, CAHPS surveys have been found to display excellent psychometric properties at the individual level and practice site level, and reliably assess the experiences of large samples of patients across diverse healthcare settings.¹³⁴ Employing standardized questions and data collection protocols, CG-CAHPS produces measurements in the following domains of patient experience:

- How Well Providers Communicate With Patients.
- Providers' Use of Information to Coordinate Patient Care

And

- Patients' Rating of the Provider

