E4.e. Data Collection (RQ-2). Upon auto-enrollment, we will extract the following variables from the electronic health record: chronic pain condition, length of time with chronic pain diagnosis, race and ethnicity, language, marital status, history of pharmacologic treatment, surgical history related to chronic pain condition, past injuries related to chronic pain condition, and length of time with current primary care provider¹³⁷. When the intervention period is initiated, all eligible patients who have any follow-up visits during this 12-month period in both study arms will be sent the questionnaires. We will also capture depression scores via the Patient Health Questionnaires -PHQ-2 and/or PHQ-9 in the EHR. Furthermore, to determine if conversations about opioid medications took place during the visit that was

informed by either the CDS or the PEATS, we will conduct a structured review of a random sample of charts from both study arms.

E5. Statistical Analysis

E5.a. Descriptive and Exploratory Analyses. We will use frequencies and means for univariate descriptive analyses. We will use chi-square tests and paired t-tests to determine whether there are differences between the two study arms; using these bivariate analyses, we will identify covariates and patient- and physician-level moderators to use in the regression models. We will also consult with our Patient Partner to ensure that all appropriate patient-level covariates are included in the final models.

E5.b. Multi-Variate Regression Models. To evaluate the effectiveness of the comparators on the selected outcomes, we will use hierarchical linear regression models to measure changes in the outcomes over time using growth modeling statistical techniques¹³⁸ and will adjust for clustering at the patient, provider, and provider office level. Growth modeling allows the testing of individual differences in outcomes over time. In this study, we will examine HRQOL and communication scores over 12 months for the two study arms. We will adjust for patient- and provider-level covariates to account for potential confounders and also to identify whether there is heterogeneity of the treatment effect (see below). The proposed models are outlined here. We will test both fixed effects and random effects.¹³⁹ (IR-3):

Primary Outcome: Model 1: Hierarchical Linear Model (Longitudinal Analysis)

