Question: Which communication strategy used during the clinical encounter is more effective in reducing pain interference over time for patients with chronic pain who were taking opioids at baseline?

Dependent variable: Pain interference as measured by PROMIS Pain Interference Score (T-Score, Continuous)

Independent variable: Comparator received, CDS vs. PEAT (Dichotomous)

Potential Covariates: Age, gender, race, ethnicity, mental health comorbidities, chronic pain diagnosis, use of other pain medications (neuropathic pain medications, NSAIDS, antidepressants), benzodiazepine use, number of office visits during intervention period, baseline HRQOL, encounter month, physician years of practice, physician gender, employment, SES.

Moderator Analyses: We will use statistical interactions examining the moderating effects of patient age, race, ethnicity, mental health comorbidities, chronic pain diagnosis, physician years of practice and physician gender on the relationship between comparator and pain interference.

Mediation Analyses: We will test whether confidence in decision and satisfaction with communication as measured by COMRADE Scores mediates the relationship between the comparator used and the pain interference outcomes.

Primary Outcome: Model 2: Hierarchical Linear Model (Longitudinal Analysis)

Question: Which communication strategy used during the clinical encounter is more effective in improving how satisfied patients feel over time after communicating with their physician about chronic pain treatment risks and benefits?

Dependent variable: CG-CAHPS

Independent variable: Comparator received, CDS vs. PEAT (Dichotomous)

Potential Covariates: Age, gender, race, ethnicity, educational level, mental health comorbidities, chronic pain diagnosis, use of other prescribed pain medications (neuropathic pain medications, NSAIDS, antidepressants) benzodiazepine use, number of office visits during intervention period, baseline HRQOL, encounter month, physician years of practice, physician gender, employment, SES.

Subgroup Analyses: We will use statistical interactions examining the moderating effects of patient age, race, ethnicity, education level, mental health comorbidities, chronic pain diagnosis; and physician years of practice and gender on the relationship between comparator and pain interference.

Secondary Outcome: Model 3: Hierarchical Linear Model

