b. Statistical Methods to Handle Missing Data and Sensitivity Analyses. If the data is not missing at random, we will use multiple imputation techniques to impute missing data for respondents (MD-2). We plan on using the *mi impute mvn* command in Stata and will generate 20 datasets compatible with the regressions planned for the final analyses. To insure that the imputation has proceeded as expected, we will visually inspect parameters from successive iterations of the model to determine if they have reached a stationary distribution. We will conduct sensitivity analyses with the dataset that includes imputed data as well as with a dataset that does not include imputed data to determine the effect of the multiple imputation and plan on reporting both results. These precautions will serve to identify autocorrelation in the imputed data and allow for proper maintenance of uncertainty in imputed values (MD-3).

c. Reporting Reasons for Dropout and Missing Data. We will drop data from patients who do not have any visits with their PCP during the intervention period or are lost to follow-up, but will compare descriptive statistics for these patients to patients with at least one visit to their PCP for sensitivity analysis (MD-4, MD-5).

E9. Project Milestones and Timeline.

During the first 3-6 months of the study project, we will train the project staff, refine the study protocol, develop the data dictionaries, and obtain IRB approval. We will hold monthly meetings with our patient partners to finalize the study design and discuss issues related to IRB approval. In Year 1, Q4, we will passively enroll eligible patients in the two study arms. In the 4 weeks before the intervention period, we will send baseline questionnaires via REDCap. In Year 2, we will begin the intervention. We will conduct weekly reports from our EHR data warehouse to determine enrolled patient visits. Enrolled patients will be sent CG-CAHPS survey one day after each primary care visit. Enrolled patients will also receive the PROMIS questionnaires once a month. We will perform monthly checks to assess the completeness of data to minimize missing data and will complete one set of interim data analyses in Year 2 to assess whether there are any issues with missing data. Full data analysis will

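### Model 2 asks about improvement in CG-CAHPS over time, but the plan names no pre-intervention CG-CAHPS score and does not adjust for one

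*Combined protocol and SAP*

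**What the plan says.** Section E6.d (item 3, Communication Questionnaire) presents CG-CAHPS under a heading that makes it a primary outcome, and calls it a survey "that is already being collected by the Cedars-Sinai Medical Network". Section E5.b commits to "hierarchical linear regression models to measure changes in the outcomes over time using growth modeling statistical techniques" and adds that "we will examine HRQOL and communication scores over 12 months for the two study arms". Within E5.b, Model 2 is labelled a primary outcome and a longitudinal analysis. It asks which strategy is "more effective in improving how satisfied patients feel over time after communicating with their physician", with "Dependent variable: CG-CAHPS". Its potential covariates end with "number of office visits during intervention period, baseline HRQOL, encounter month, physician years of practice, physician gender, employment, SES". Baseline HRQOL is listed; a prior CG-CAHPS score is not.

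On timing, E4.c sends CG-CAHPS one day after the office visit in both arms. E9, after stating that the intervention begins in Year 2, says: "Enrolled patients will be sent CG-CAHPS survey one day after each primary care visit". E4.c and E9 also mention baseline questionnaires without naming the instruments. Milestone B12 in Attachment C-R, the baseline-questionnaire milestone, names PROMIS only. The variables to be extracted from the health record at auto-enrolment (E4.e) do not include CG-CAHPS.

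The section on threats to internal validity (F) relies on whether communication scores rise. If HRQOL and prescribing improve without such a rise, outside events may be held responsible.

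**The concern.** A model of improvement needs a level to improve from. PEAT materials go out two days before the visit and CDS alerts can fire during it, so a patient's first study CG-CAHPS normally follows a visit already open to the intervention. If the effect is immediate, a slope that starts there misses it. Section F's reasoning from a rise in communication scores has the same gap, because no starting level is named.

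CG-CAHPS is also used here as a measure of how physicians communicate (E6.d), and physicians, or their offices, are randomised. Some arm difference in prior communication quality is expected by chance. A pre-period score would show it, adjust for it, and remove part of the between-PCP variance from the standard error. The plan gives no power calculation for CG-CAHPS (E5.c covers pain interference only), so any cheap precision for this outcome has value.

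**Working it through.** **1. What the slope can show.** Write Model 2 in its simplest form, with t = 0 at the first surveyed visit:

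score = a + b·arm + c·t + d·arm·t + random effects

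An effect present at the first exposed visit enters b. The growth contrast d holds only the change after that. Without a pre-intervention level, b combines the immediate effect with any chance difference in where the PCPs started. Section D2 requires only one visit in the follow-up year, so a patient may supply a single CG-CAHPS score and no within-patient change.

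**2. Inputs for size.**
- PCPs: 80 (E4.d), split 50/50 (milestone B9), so about 40 per arm if PCPs are the unit.
- Patients per PCP, m: 640/80 = 8 (E5.c); 960/80 = 12 (E5.c); 4,000 × 30% = 1,200 and 1,200/80 = 15 (E4.d). Range 8 to 15.
- ICC for CG-CAHPS: not given. The plan's 0.02 is for pain interference. Assumed 0.02 to 0.10.
- r, the correlation of the observed prior PCP mean with the PCP effect in the trial: not given. Assumed 0.5 to 0.8.

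The plan has no precision figure of its own for CG-CAHPS to reproduce.

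**3. Chance imbalance.** The SD of the arm difference due to PCP effects alone is √(2·ICC/40), in units of the outcome SD:

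| ICC | SD | 95% range (±1.96 SD) |
|---|---|---|
| 0.02 | 0.032 | ±0.06 |
| 0.05 | 0.050 | ±0.10 |
| 0.10 | 0.071 | ±0.14 |

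For scale, the only effect size in the plan, for pain interference, is 0.3 SD.

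**4. Gain from adjusting for the prior PCP mean.**

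Variance ratio = [ICC(1 − r²) + (1 − ICC)/m] / [ICC + (1 − ICC)/m]

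| ICC | m | r | Variance ratio | SE ratio | Fall in SE |
|---|---|---|---|---|---|
| 0.02 | 8 | 0.5 | 0.1375/0.1425 = 0.965 | 0.982 | 1.8% |
| 0.05 | 8 | 0.7 | 0.14425/0.16875 = 0.855 | 0.925 | 7.5% |
| 0.10 | 15 | 0.8 | 0.096/0.160 = 0.600 | 0.775 | about 22% |

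**5. Noise in the prior mean.** If 0.7 is instead the correlation between true PCP effects in the two periods, the observed mean of k prior surveys is a weaker predictor. Its reliability is ICC/[ICC + (1 − ICC)/k], and r² is multiplied by it.
- ICC 0.05, k = 20: reliability 0.05/0.0975 = 0.513; r² = 0.49 × 0.513 = 0.251; variance ratio 0.926; SE falls 3.8%.
- ICC 0.05, k = 50: reliability 0.725; r² = 0.355; SE falls 5.4%.
- ICC 0.02, k = 20: reliability 0.290; r² = 0.142; SE falls about 1%.

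**The case against.** A reader might infer that the primary comparison is biased, or that chance differences between PCPs enter it unaccounted for. The documents do not support this. Assignment is random, so a comparison of post-intervention levels is unbiased without a baseline. E5.b already adjusts for clustering at provider and office level, so between-PCP differences are carried in the standard error.

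A reader might also infer that baseline CG-CAHPS is ruled out. It is not. The baseline questionnaires in E4.c and E9 are generic, and E4.c refers for detail to the Outcome Measurement section, which covers CG-CAHPS. The data-elements table (Appendix I, Table 3) is not in the supplied text. Model 2's covariates are only potential, and E5.b allows provider-level adjustment. So the supportable statement is that no baseline CG-CAHPS is named. That still leaves the adjustment unspecified, and B12 points to PROMIS alone.

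Three further objections stand as limits:
- The randomised unit is unsettled. E4.b says provider level but also speaks of assigning offices, and B9 randomises offices. The formulas above have no office variance and assume PCPs are the unit.
- The plan says the network collects the survey, but gives no start date, volume per PCP or means of linkage. Respondents across the network may also differ from opioid-treated patients.
- Not every first visit is actually touched. CDS alerts fire only on set triggers, and patients may opt out of PEAT materials.

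**Conclusion.** The point holds as one of precision and interpretation, not of validity. No pre-intervention CG-CAHPS is named, so Model 2's improvement question and section F's inference from rising communication scores lack a starting level. An immediate effect would sit in the intercept.

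The precision at stake is modest and rests on assumptions: a fall in standard error of about 2% to 22% over the ranges shown, 7.5% in the middle case, and about 4% in that case if each prior mean rests on only 20 surveys.

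It is tempting to invert the middle variance ratio (1/0.855 = 1.17) and call it 17% more patients. That would hold only if PCPs increased in the same proportion, and the plan has 80. The gain is better left as a change in standard error. The change is worth making because it is cheap and it allows the model to answer the question it poses.

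**What to change.** Prespecify in Model 2 a fixed covariate equal to each PCP's mean CG-CAHPS communication score before randomisation (milestone B9, projected 7/30/2017), or at the latest before the intervention starts (milestone C1, projected 1/1/2018), taken from the routine network survey. Add the patient's own prior score where it can be linked, with an indicator for patients who have none. State the effect to be reported so that a difference already present at the first exposed visit counts towards it.

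If no pre-period data can be extracted, define the Model 2 effect as the arm difference in CG-CAHPS level over follow-up, not as change, and remove from section F the inference that depends on an increase in communication scores.

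The cost is one data pull and one covariate, with no added patient burden. It depends on first confirming that the routine data can be extracted by PCP, and with how many surveys each.

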E4.b. Unit of Randomization. We will randomize the study on the provider level. We will use a random number generator to assign offices to study arms, and will employ multi-level hierarchical models to adjust for clustering within the physician level, described in more detail below.

E4.c. Study Design Overview.

We will auto-enroll all eligible patients to participate in the pragmatic trial and will administer baseline questionnaires as further detailed in the Recruitment Procedures and Outcome Measurement sections below. Patients within the physicians randomized to the CDS arm will not receive the PEAT materials; their physicians will receive the Choosing Wisely alerts via the EHR (Epic Systems, Verona, Wisc.) when appropriate. Patients within the physicians randomized to PEAT will receive the engagement materials via REDCap two days prior to their PCP office visit, supplemented by duplicate paper copies sent via express delivery. For both study arms, patients will receive Clinician and Group Consumer Assessment of Healthcare Providers and Systems (CG-CAHPS) one day after their office visit. They will receive the PROMIS questionnaires every month throughout the study period. We will track follow-up visits through the EHR reports. In all instances, patients may refuse to participate by either not using the PEATs sent via REDCap, or not completing outcome questionnaires.

3. Analysis, Dissemination, and Implementation. In Year 3, we will conduct the statistical analyses and will collaborate with our patient partners to determine the implications of the study results. We present our Dissemination and Implementation plan in full detail below.

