E5.c. Power Calculations. Guided by previous work in chronic pain interventions,¹⁴⁰ we calculated sample size using an intracluster correlation coefficient of 0.02, an α level of 0.05, 90% power, and detection of a mean (SD) difference of 0.3 standard deviations on the PROMIS Pain Interference scale. We calculated a sample size of 320 patients per study arm, for a total of 640 patients. To compensate for predicted loss to follow-up, multiple variables in the final multi-level models, as well as sub-group analyses, we inflated the sample size by 50% to 960. Since we will be examining the effect of the interventions on a variety of sub-groups within the study sample, such as diagnoses of mental health conditions, race, ethnicity, gender, and chronic pain diagnosis, we will be adequately powered to detect meaningful differences. In our original proposal, we calculated a sample size of 320 patients per study arm for a total of 640 patients. To compensate for predicted loss to follow-up and non-response we had inflated the recruitment target size by 50% to 960. Under the current modification – and given the absence of changes to the assessment schedule, the estimated intracluster correlation coefficient, and the expected mean difference - the sample size required to adequately power the analysis remains unchanged. We believe the recruitment target will also remain consistent, and potentially even fall due to the ability of study staff to call passively enrolled patients and remind them to respond to assessments. We therefore anticipate being adequately powered to detect meaningful differences between the two arms.

E6 Heterogeneity of Treatment Effect (HT-1, HT-3, HT-4)

After reviewing the literature and consulting with our patient partners, we identified specific subgroups we plan to analyze to identify whether there is a heterogeneity of the treatment effects. Below we detail our planned sub-group analyses, our hypotheses, and our plans for statistical analysis for each subgroup. In order to address the problem of multiplicity, a Bonferroni correction will apply to all analyses.

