Attachment C-R: Milestone Schedule

	Milestone Name	Description	Projected Completion Date
A	Project Start Date	-	3/13/2017
B1	Stakeholder engagement meeting	Stakeholder engagement kick-off meeting	3/30/2017
B2	Patient eligibility data pulls	EIS Data Analyst to create a list of eligible patient population	4/30/2017
B3	Study protocol completed	Final trial protocol completed - submit a copy to PCORI	5/30/2017
B4	Patient eligibility data pulls	EIS Data Analyst to finalize list of eligible patient population and other data pulls	5/30/2017
B5	IRB Approval Obtained	Obtain IRB approval for study and submit approval letters to PCORI	7/30/2017
B6	DSMB Meeting 1	Set safety protocols and standards for data safety monitoring	7/30/2017
B7	Integration of questionnaires into patient portal	EIS Data Analyst to integrate questionnaires into MyCSLink	7/30/2017
B8	Select and register project at appropriate site for the study design (Clinicaltrials.gov, RoPR, or other as approved by PCORI before study start date)	Study Identification Number and the Primary Research Completion Date must be sent to PCORI.	7/30/2017
B9	Randomization of clinic sites	Randomization of Cedars-Sinai network offices completed; 50% to CDS arm and 50% to PEAT arm of trial	7/30/2017
B10	Passive patient recruitment begins	Passive data enrollment begins for study participants (N=960) / Study begins	8/1/2017
B11	Pharmacy data collection begins	EIS Data Analyst to begin pull data for passively enrolled patients on pharmacy data for data monitoring purposes	8/1/2017
B12	Patient baseline questionnaires	Enrolled patients begin filling out PROMIS patient reported outcome questionnaires	8/1/2017
B13	Stakeholder engagement meeting	Stakeholder engagement meeting to update on IRB submission and patient eligibility protocols and baseline data collection	8/31/2017
B14	Engagement Update	For the 6-month time intervals (i.e., 6 months, 18 months, 30 months, etc. but not at 12 months or 24 months), provide specific examples of the impact of engagement on project activities during the reporting period. Report this in the Engagement Report section of the PCORI interim progress report.	9/13/2017
B	Report Submission	Submit 6-month Interim Progress Report, Using PCORI Interim Progress Report Template	9/13/2017
C1	Study intervention begins	Study intervention begins	1/1/2018
C2	Stakeholder engagement meeting	Updates on study implementation	2/28/2018

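### E5.a compares two unpaired, cluster-randomised arms with paired t-tests and chi-square tests with no stated clustering adjustment, then uses arm differences to choose covariates and moderators

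*Combined protocol and SAP*

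**What the plan says.** E5.a (Descriptive and Exploratory Analyses) sets out the arm comparison: "We will use chi-square tests and paired t-tests to determine whether there are differences between the two study arms". The same sentence gives its purpose: "using these bivariate analyses, we will identify covariates and patient- and physician-level moderators to use in the regression models". The Patient Partner is also consulted on patient-level covariates.

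Clustering is addressed elsewhere, and only for the regressions. E4.b says the analysts "will employ multi-level hierarchical models to adjust for clustering within the physician level"; E5.b says the hierarchical models "will adjust for clustering at the patient, provider, and provider office level". E5.a mentions no such adjustment.

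On the unit of allocation, E4.b says both "We will randomize the study on the provider level" and "We will use a random number generator to assign offices to study arms". Row B9 of the Milestone Schedule (Attachment C-R) also refers to offices, with "50% to CDS arm and 50% to PEAT arm of trial". No matching of physicians, offices or patients is described.

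E5.b lists 15 covariates for Model 1 but calls them only potential. Moderators are named outright: seven for Model 1 in E5.b, including physician gender and years of practice, and the subgroups in E6 (race/ethnicity, mental health diagnosis, gender).

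**The concern.** Three things are wrong with this step.

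- **The paired test does not fit the design.** Each physician belongs to one arm and patients follow their physician. A paired t-test would need an arbitrary matching of CDS patients to PEAT patients, its result would depend on that matching, and it cannot be run when the arms differ in size.
- **Clustering is not mentioned.** A plain chi-square or t-test on patient rows treats patients of one physician as independent. The effect is largest for physician characteristics, which are constant within a physician.
- **The selection rule is unsound whichever test is used.** Under randomisation, an arm difference in a baseline variable is chance. It does not show that the variable predicts pain interference, which is the reason to adjust for it. It also says nothing about effect modification, which needs a treatment-by-covariate interaction.

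Because the covariates are only potential, E5.a plus the Patient Partner's advice is the only stated route from the candidate list to the final models. At stake are the prespecification of the adjusted analysis and its precision.

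**Working it through.** **Inputs.** ICC, alpha and power from E5.c: "an intracluster correlation coefficient of 0.02, an α level of 0.05, 90% power" (two-sided alpha assumed). Also from E5.c: 0.3 SD difference, 320 per arm, 640 in total, inflated to 960. From E4.d: 80 PCPs and about 4,000 eligible patients.

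**The plan's own figure.** The plan gives no error rate for this step. The nearest figure is the sample size. Without clustering, n per arm = 2(1.960 + 1.282)²/0.3² = 234. Multiplying by 1 + (m − 1) × 0.02 gives 267 at m = 8 and 286 at m = 12. The stated 320 implies 320/234 = 1.368, so m = 1 + 0.368/0.02 ≈ 19.4. The plan does not state m, so 320 can be neither confirmed nor called wrong; 19.4 is carried below as one further cluster size.

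**True size of an unclustered 5% test.** Size = 2[1 − Φ(1.96/√DE)]. For a patient variable DE = 1 + (m − 1) × ICC. For a physician variable tested on patient rows DE = m. Cluster sizes are taken as equal. Examples at m = 8:

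- Patient variable, ICC 0.02: DE = 1.14, 1.96/√1.14 = 1.836, size = 6.6%.
- Physician variable: DE = 8, 1.96/√8 = 0.693, size = 49%.

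| Patients per PCP | DE at ICC 0.02 | Size, ICC 0.02 | Size, ICC 0.01 to 0.10 | Physician factor on patient rows |
|---|---|---|---|---|
| 8 (640/80) | 1.14 | 6.6% | 5.8% to 13.3% | 49% |
| 12 (960/80) | 1.22 | 7.6% | 6.3% to 17.6% | 57% |
| 19.4 (implied by 320) | 1.368 | 9.4% | 7.2% to 24.5% | 66% |
| 50 (4,000/80) | 1.98 | 16.4% | 10.8% to 42% | 78% |

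The 0.02 was set for sizing the Pain Interference comparison. The plan gives no covariate ICC, so 0.02 is an assumption here and 0.01 to 0.10 an assumed range.

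**Expected false differences among the 15 Model 1 candidates.** Take 13 patient-level candidates at ICC 0.02 and 2 physician-level candidates tested on patient rows. At m = 8: 13 × 0.066 + 2 × 0.488 = 1.8. At m = 12: 13 × 0.076 + 2 × 0.572 = 2.1. Correctly sized tests give 15 × 0.05 = 0.75.

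**What reaches the primary model.** This was simulated with 80 clusters, 4,000 runs, no treatment effect, five baseline covariates with an assumed slope of 0.3 each, and a cluster-adjusted outcome model.

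- At m = 12 and covariate ICC 0.02, arbitrarily paired and unpaired tests flagged covariates equally often (7.9% each). Tests on cluster means stayed near 5%.
- After selection by the unclustered tests, the outcome model was unbiased, with type I error between 0.8% and 4.4% across the settings tried. With all covariates fixed in advance it was 4.6% to 5.4%.
- At m = 12 and covariate ICC 0.02, the SD of the treatment estimate was 0.081 after selection and 0.071 with the fixed set. The variance ratio is (0.081/0.071)² ≈ 1.30, about 30% more variance under the assumed slopes.

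**The case against.** The strongest reply is that this is a screening step in a section headed descriptive and exploratory, and that it does not damage the primary result. Much of that stands.

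- A reader might infer that false arm differences make the primary analysis invalid. The documents do not support this. E5.b keeps the clustering adjustment in the models, and a falsely flagged baseline covariate is just one more adjustment variable from a list named in advance. The simulation found no bias and no inflation.
- The pairing error adds nothing to the false-positive rates, which come from ignoring clustering. The precision loss comes from selecting on arm differences at all. Extra false flags, if anything, move the model towards the full list.
- Moderators are named in E5.b and E6, so the physician-level rates do not alter the use of physician gender and years of practice as moderators in Models 1 and 2.
- E5.a does not say that the chi-square tests ignore clustering or that physician factors are tested on patient rows. An analyst could compare the 80 physicians directly.
- The 16% needs all 4,000 eligible patients. That may suit variables drawn from the EHR, but E4.d expects only about 30% to complete all questionnaires.

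What remains is that the named test cannot be applied, no final covariate set exists, and the stated selection rule is wrong in principle and at odds with the plan's own moderator lists. Nor can the paired test be read as a before/after comparison, since the sentence refers to differences between arms.

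**Conclusion.** The point holds as a specification fault in E5.a that should be corrected. The paired t-test has no valid form in this design. Testing arm differences is not a sound way to choose covariates or moderators.

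The error rates are conditional: about 6.6% to 16% for patient variables if clustering is ignored and their ICC is 0.02, and 49% to 78% for physician factors if they are tested on patient rows, with equal clusters and the PCP as the unit. If offices are the unit, clusters are presumably fewer and larger and the rates higher, but the number of offices is not given.

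The consequence is a covariate set that depends on the data, room for analyst choice and lost precision. It is not an inflated primary type I error. That reassurance covers baseline covariates only. One Model 1 candidate, the count of office visits during the intervention, is measured after randomisation. A real effect of the intervention on visits could bring it into the primary model through this rule.

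**What to change.** Rewrite E5.a as follows.

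1. Delete the paired t-tests. Describe baseline balance with means or percentages by arm and standardised differences.
2. If a test is wanted, use an independent-sample comparison that accounts for the randomised cluster, and compare physician gender and years of practice with the physician as the unit. First reconcile the provider and office statements in E4.b and milestone B9.
3. Fix the covariates for each model in advance on prognostic grounds, including baseline PROMIS score. Use baseline variables only, which removes visits during the intervention as an adjustment term.
4. Keep moderators to those named in E5.b and E6, assessed by interaction. State that arm-difference tests select neither covariates nor moderators.

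The cost is about one paragraph of wording and a fixed covariate list. It needs no extra data and places no burden on patients.
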